## 7.1 Duration of Therapy

Treatment may continue for the 3-cycle treatment phase or until:

- Inter-current illness that prevents further administration of treatment
- Unacceptable adverse event(s) of the study regimen despite appropriate dose reduction and best supportive management
- Patient decides to withdraw from the study
- Noncompliance with study regimen or follow up appointments
- General or specific changes in the patient's condition render the patient unacceptable for further treatment in the judgment of the investigator.

The principal investigator will be notified and a case report form will be completed including the reason for study removal and the date the patient was removed. The patient should be followed up per protocol.

## **8. STATISTICAL CONSIDERATIONS**

### **8.1 Study Design/Study Endpoints**

The primary endpoints will be the disease progression-free rate at the end of the treatment phase 1 and safety of the combination of 5-AZA and ATRA. Disease progression is defined by composite of PSA or radiographic progression relative to period baseline (start of treatment phase 1), whichever occurs first. PSA levels will be measured on day 1 of each cycle. For assessment of PSA progression, see section 3.2.1 above. CT A/P and bone scan will be performed every 3 cycles. For assessment of radiographic progression, see section 3.2.2 above. Safety will be assessed by the recording of adverse events, monitoring of vital signs and physical examinations, safety laboratory evaluations, and 12-lead ECG. Adverse events will be graded per the Common Terminology Criteria for Adverse Events (CTCAE) version 4.0. Therapy will be continued at the original dose if the adverse event is grade 0-2. For grade 3-4 toxicities, therapy will be held until improvement of symptoms to grade 2 or below. The dose will then be reduced by 25% of original for each episode. A maximum of 2 dosage reductions will be allowed. The third occurrence will result in removal of the patient from the study.

The secondary endpoints will be time to tumor progression from start of treatment phase 1 and the measurement of dormancy biomarker levels in relation to disease states: tumor progression and disease progression. To determine the relation between dormancy biomarkers and disease states, every 3 cycles, we will measure the dormancy biomarkers, TGF $\beta$ 2, BMP7, BMP4, GAS6, retinoic acid, NR2F1, in BM aspirates and peripheral blood.

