## 3. STUDY DESIGN

### **3.1 General Design**

This is a prospective, open-label, randomized, pilot study of reprogramming therapy in patients with recurrent PCa based on rising PSA only. Reprogramming therapy will include 5-azacitidine and all-trans retinoic acid. Expected duration of subject participation is 24 months.

All study will be assigned in a 1:1 randomization using computer random number generator to either the '5-AZA+ATRA' group or the 'no therapy' group. All enrollees will receive Leuprolide 7.5 mg x 1 on Day 1. On Day 29, they will initiate treatment phase 1. During this phase, patients in the '5-AZA + ATRA' group will receive treatment on a 28-day cycle, in the absence of prohibitive toxicities, for 3 cycles. During treatment phase 2, the 'no therapy' group will receive 5-AZA + ATRA on a 28-day cycle, in the absence of prohibitive toxicities, for 3 cycles. The treatment effect will be determined via comparing the intra-individual disease progression outcome at the end of the treatment phase 1, with period effect being separated through randomization. After treatment phase 1 and phase 2, all patients will be followed for a total of 24 months from the start of the study or until the events leading to discontinuation as outlined in Section 7.1 are observed. 5-AZA will be given subcutaneously on days 1-5 at a dose of 40 mg/m^2. ATRA, dosed at 45 mg/m^2 daily (divided into 2 doses), will be taken orally on days 3-7 of each cycle.

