#### **3.2.1 PSA Progression**

PSA Progression is as defined by PCWG2 criteria. Baseline PSA will be defined as the serum PSA level measured prior to start of treatment.

In patients who have a decline in PSA value from baseline, progression is defined by:

- An increase in PSA by 25% above the nadir, AND
- An increase in PSA by a minimum of 2 ng/ml, or an increase in PSA to the pre-treatment PSA value, AND
- Confirmation by a second PSA at least 3 weeks apart, AND
- There is no objective evidence of disease response.

In patients whose PSA value has not declined from baseline, progression is defined by:

- An increase in PSA by 25% above either the pre-treatment level, or the nadir PSA level (whichever is lowest), AND
- An increase in PSA by a minimum of 2 ng/ml, AND
- Confirmation by a second PSA at least 3 weeks apart, AND
- There is no objective evidence of disease response.

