### **8.2 Sample Size and Accrual**

The primary endpoint is disease progression free rate at the end of treatment phase 1. Disease progression is defined as either PSA progression or radiographic progression relative to baseline. The baseline value is defined as the PSA level at the beginning of treatment phase 1 (Day 29 of study). The previous Phase II studies on 5-AZA and ATRA individually demonstrated their efficacy in delaying PSA rise among prostate cancer patients. Preclinical in-vivo study demonstrated that in adjuvant setting following primary tumor surgery, animals treated with the drug combination for 4 weeks have 73% reduction on the median cell count of disseminated tumor cells in lung comparing to control animals (Personal communications between [name] and [name]).

Thus, we assume the difference in progression free rates at end of the treatment periods between drug combination and no-therapy ranges between 30% to 60% and listed various scenarios of progression-free rates in Table 1. We use McNemar test statistic to calculate the range of sample size required to differentiate the treatment from no-therapy under each scenario. The maximum sample size is required when the PSA rise is independent in the two treatment periods for the same patient. The minimum sample size is required when the PSA progression status in the two treatment periods is highly concordant. With the planned 20 patients in total, we would have >80% power to detect the difference of PSA progression rate of 20% vs 60%, with two-sided type I error of 10%. All calculation was done using PASS software.

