### **8.4 Data analyses**

Analysis on efficacy and safety:

Patients will receive at least 8 weeks of treatment in order to be eligible for efficacy analysis. Patients who discontinued due to toxicity after 8 weeks of treatment will be included in efficacy analysis. Descriptive statistics such as mean/median/range and frequency will be provided for continuous and categorical variables separately, and the distributions of period baseline variables are contrasted between 5-AZA+ATRA and placebo using Wilcoxon statistics and Fisher's exact test statistics for continuous and categorical variables separately. Waterfall plot will be provided for PSA change relative to period baseline for all patients for each treatment arm and period. Analysis will follow the two-step procedure prescribed in for randomized crossover study for binary endpoint. To test for carryover effect, Wilcoxon rank-sum test stratified by prior PSADT will be performed to assess whether the sum of outcome variables from both periods is different between the randomization arms. If the test yields insignificant results, a similar test will be performed to compare the within-patient outcome difference between period 1 and 2 between the randomization arms to assess the treatment effect. If the carryover effect is significant, the primary analysis will be based on the progression free rates at the end of first treatment period using Chi-square test. In addition, general linear mixed model will be applied to assess the treatment effect, carryover effect, and period effect, adjusting for the stratification factor prior PSADT. The time to disease progression is defined as time to either PSA progression or radiographic progression whichever occurs first since discontinuation of ADT. Time to event endpoints will be summarized using Kaplan-Meier method. The time to event endpoints will be estimated using rank preserving failure time model (RPFTM) to obtain the counter-factual event times assuming cross-over did not occur (R package "rpfstm").

Descriptive summary will be provided for the safety endpoints. All patients who received at least one dose of study drug (treated set) will be included in the safety analysis.

Correlative analysis and biomarkers:

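### The only baseline defined for progression is the start of Treatment Phase 1, yet the crossover analysis and the sample size need a progression outcome in Phase 2 as well

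*Combined protocol and SAP*

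**What the plan says.** **Baseline.** Section 8.1 defines the composite as PSA or "radiographic progression relative to period baseline (start of treatment phase 1), whichever occurs first". Section 8.2 adds: "The baseline value is defined as the PSA level at the beginning of treatment phase 1 (Day 29 of study"). Section 3.2.1 is looser: "Baseline PSA will be defined as the serum PSA level measured prior to start of treatment", with no period named, and 3.2.2 ties baseline imaging to the start of treatment in the same way. PSA progression is measured from a nadir (3.2.1) and target-lesion progression from the smallest sum since treatment began (3.2.2.1). Neither reference is limited to a period.

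**Endpoint.** In 8.2 the Day 29 definition accompanies an endpoint at the end of Phase 1: "The primary endpoint is disease progression free rate at the end of treatment phase 1".

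**Crossover.** Section 3.1 states: "During treatment phase 2, the 'no therapy' group will receive 5-AZA + ATRA on a 28-day cycle". Section 7.1 does not list progression among the reasons to stop treatment.

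**Analysis.** Section 8.4 first tests carryover on the sum of the two periods' outcomes, at an unstated level. If that is not significant, a similar test is used to "compare the within-patient outcome difference between period 1 and 2 between the randomization arms". If it is significant, first-period rates are compared by chi-square. A mixed model for treatment, period and carryover is added. The same section says: "Waterfall plot will be provided for PSA change relative to period baseline for all patients for each treatment arm and period".

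**Sample size.** Section 8.2 uses the McNemar test and states: "The maximum sample size is required when the PSA rise is independent in the two treatment periods for the same patient". It claims more than 80% power with 20 patients at 20% vs 60%, two-sided 10%.

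**The concern.** The carryover test, the within-patient test, the mixed model and the McNemar calculation each use two progression outcomes per patient. The plan says what the first is measured against, but not the second. The only dated reference available is Day 29.

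Take a patient in either arm with confirmed progression in Phase 1. Against Day 29, or against a nadir or smallest sum reached in Phase 1, he starts Phase 2 above the threshold, or with the new lesion already on the scan. Unless the PSA falls back, he is scored as progressed in Phase 2 whatever he receives there. The most informative patient in the control-first arm, who progresses off drug and is then stable on drug, could not be recorded. Nor could the mirror-image patient in the drug-first arm.

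At stake are the size of the within-patient estimate, the meaning of the carryover test, and the independence case on which the upper sample-size figure rests. The trial is open-label, so a scoring rule left unstated could be settled after outcomes are known.

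**Working it through.** **Inputs from the plan.** 20 patients, 1:1, so 10 per arm (3.1, 8.2); two-sided 10% (8.2); rates of 20% and 60% (8.2). Section 8.2 calls these both progression-free and progression rates. They are taken here as progression-free: 60% on drug, 20% on no therapy. The other direction is in step 5.

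**Assumptions.** No true carryover; periods otherwise independent; carryover test at 10%; rank-sum tests without the PSADT stratification.

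**1. The plan's own figure.** Let p10 be the proportion progression-free on drug only, and p01 the proportion progression-free off drug only. Then

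n = [1.645·√(p10+p01) + 0.842·√(p10+p01−(p10−p01)²)]² / (p10−p01)².

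- Independent periods: p10 = 0.6×0.8 = 0.48 and p01 = 0.4×0.2 = 0.08, so n = (1.231+0.532)²/0.16 = 19.4.
- Full concordance: p10 = 0.40 and p01 = 0, so n = (1.040+0.412)²/0.16 = 13.2.

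Table 1 in section 8.2 gives 14-19. Power at 20 patients under independence is 81%, which matches the stated claim. So the plan's figure is reproduced when each period's outcome can vary freely.

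**2. Day 29 kept in Phase 2, progression permanent.**

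- Control-first: Phase 1 rate 0.20; Phase 2 rate on drug 0.20×0.60 = 0.12, not 0.60.
- Drug-first: Phase 1 rate 0.60; Phase 2 rate off drug 0.60×0.20 = 0.12, not 0.20.
- Within-patient effect: [(0.60−0.12) − (0.20−0.12)]/2 = 0.20. With a baseline per period it is [(0.60−0.20) − (0.20−0.60)]/2 = 0.40.
- Mean sum of the two periods: 0.72 drug-first vs 0.32 control-first, instead of 0.80 vs 0.80. An effective drug therefore looks like carryover.

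**3. McNemar on the same reading.** Each discordant pair can arise in one arm only: p10 = (0.48+0)/2 = 0.24 and p01 = (0+0.08)/2 = 0.04. Then n = (0.8704+0.4123)²/0.04 = 41.1, so 42 patients. Power at 20 is Φ[(√20×0.20−0.870)/0.490] = Φ(0.05) = 52%.

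**4. The planned two-step analysis, simulated** (40,000 trials per scenario).

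| | Baseline per period | Day 29 kept, half of Phase 1 progressors can be scored progression-free again | Day 29 kept, permanent |
|---|---|---|---|
| Within-patient effect | 0.40 | 0.30 | 0.20 |
| Power, within-patient test alone | 83% | 74% | 67% |
| Carryover test falsely positive | 10% | 19% | 48% |
| Power, first-period chi-square | 62% | 61% | 62% |
| Power, full two-step procedure | 80% | 77% | about 75% |

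The middle effect can be checked by hand. The control-first Phase 2 rate is 0.12+0.8×0.5×0.6 = 0.36 and the drug-first rate is 0.12+0.4×0.5×0.2 = 0.16, so the effect is [(0.60−0.16) − (0.20−0.36)]/2 = 0.30.

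**5. Sensitivity** (baseline per period, then Day 29 kept and permanent).

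- Progression-free 80% vs 40%: effect 0.40 to 0.20, within-patient power 83% to 67%, false carryover 10% to 32%, two-step power 80% to 76%.
- 60% vs 20% with a latent between-period correlation of 0.5: within-patient power 93% to 76%, false carryover 10% to 45%, two-step power 89% to 82%.
- No drug effect (both rates 40%, or both 20%), Day 29 kept and permanent: the estimate stays at 0 and the within-patient test rejects in 6-10% of trials. The two-step procedure rejects in 12-16%, against 12-14% with a baseline per period.

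**The case against.** A reader might infer that the plan judges progression against Day 29 in both periods. The documents do not say so. The wording in 8.1 and 8.2 accompanies an endpoint at the end of Phase 1, for which Day 29 is the right reference. The term period baseline, and its use in 8.4 by arm and period, suggest that one baseline per period was intended. This stands: the defect is a Phase 2 reference that is missing and at odds with the only definition given, not a declared rule for both periods. But 8.4 supplies no definition, so the term falls back on 8.1.

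The pre-treatment wording in 3.2.1 could be read as giving a control a fresh baseline before his Phase 2 drug. It would not do the same for a drug-first patient, whose treatment started in Phase 1, so it does not settle the matter for both arms.

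A reader might also take 83% to 67% as the trial's loss of power. That is the within-patient test alone. When the carryover test is positive, the analysis moves to first-period rates, which a Phase 2 baseline cannot affect, and the procedure as a whole loses about 5 points. This stands too, although the rescue sends nearly half of trials to a test with about 62% power.

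Finally, the documents do not support a reading that the problem favours the drug or affects only controls. Both arms are locked in, and the estimate shrinks toward zero.

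**Conclusion.** The point holds as an undefined Phase 2 baseline with a conditional consequence, and should be fixed. If Day 29 is applied in Phase 2 and progression does not reverse, the within-patient effect is halved, within-patient power drops by about 16 points, false carryover rises to about 48%, and two-step power drops by about 5 points. Partial reversal gives roughly half of the loss in effect and a smaller loss elsewhere. If per-period baselines are used, the plan's power figure stands.

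The bias is toward no effect. Type I error of the within-patient test is not inflated, and the end-of-Phase-1 rates and the fallback chi-square are unaffected. The figures rest on the assumptions listed above; the 10% carryover level and the share of progressors who could be scored progression-free again are not in the plan. The reason to act even if per-period baselines were intended is that the choice moves the estimate between 0.20 and 0.40 in an open-label trial.

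**What to change.** Amend 8.1 and 8.2, with matching text in 3.2.1 and 3.2.2:

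- Keep Day 29 as the Phase 1 baseline and as the reference for time to progression.
- For the Phase 2 outcome, in both arms, use the PSA on day 1 of Phase 2 and the restaging scan at the end of Phase 1 as baseline.
- Restart the PSA nadir and the smallest-sum reference at that point. Otherwise a Phase 1 nadir could still mark a Phase 1 progressor as progressed.
- Assign to Phase 1 a PSA rise first seen in Phase 1 but confirmed after the switch. Section 3.2.1 requires confirmation at least 3 weeks later, so this will occur for rises at the last Phase 1 measurement.

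The cost is wording only. Table 8 already schedules PSA every 4 weeks and CT and bone scan every 12 weeks in the treatment phases (taken here to cover both arms in both phases), so no new visit or scan is needed.

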### 6.2.1 Hematologic Toxicities

**Table 6. Hematologic toxicity dose reductions for 5-AZA**

Grade	ANC a	Platelets	Hemoglobin	Action
1	<LLN to 1,500/ $\mu$ L	<LLN to 75,000/ $\mu$ L	< LLN to 10 g/dL	None
2	1000-1499/ $\mu$ L	50,000 to 74,999/ $\mu$ L	8 – 10 g/dL	None
3	500-999/ $\mu$ L	25,000 to 49,999/ $\mu$ L	< 8 g/dL	
-1st Occurrence: Hold current dose until ANC <math>\geq</math> 1,000/<math>\mu</math>L, platelets <math>\geq</math> 50,000/<math>\mu</math>L, and hemoglobin <math>\geq</math> 8 g/dL. Do not replace missed doses. Restart next treatment at 30 mg/m^2 dose.
 
-2nd Occurrence: Discontinue protocol therapy.
 
-If therapy held > 3 weeks: Discontinue protocol therapy.

4	<500/ $\mu$ L	<25,000/ $\mu$ L	Life-threatening consequences; urgent intervention indicated	
-1st Occurrence: Hold current dose until ANC <math>\geq</math> 1,000/<math>\mu</math>L, platelets <math>\geq</math> 50,000/<math>\mu</math>L, and hemoglobin <math>\geq</math> 8 g/dL. Do not replace missed doses. Restart next treatment at 30 mg/m^2 dose.
 
-2nd Occurrence: Discontinue protocol therapy.
 
-If therapy held > 3 weeks: Discontinue protocol therapy.

aNote: G-CSF (Filgrastim) 5 mcg/kg/day may be added for low ANC on day of treatment BEFORE a dose reduction is instituted at treating physician's discretion. This will be continued until anticipated nadir has passed and ANC <math>\geq</math> 1000. Neulasta® is NOT allowed.
				

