### 6.2.2 Non-hematologic toxicities

5-AZA will be continued at the original dose if the adverse event is grade 0-2. For grade 3-4 toxicities related to study drug, 5-AZA will be held until improvement of symptoms to grade 2 or below. After the first episode, the dose will be reduced by 25%. After the second episode, the protocol therapy will be discontinued. The investigator will determine whether the toxicity is related to study drug. The investigator may prescribe any concomitant medications as necessary, except for other anti-cancer therapy, for the management of adverse effects.

ATRA will be continued at the original dose if the adverse event is grade 0-2. For grade 3-4 toxicities related to study drug, ATRA will be held until improvement of symptoms to grade 2 or below. After the first episode,

the dose will be reduced by 25%. After the second episode, the protocol therapy will be discontinued. The investigator will determine whether the toxicity is related to study drug. The investigator may prescribe any concomitant medications as necessary, except for other anti-cancer therapy, for the management of adverse effects.

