**Table 7. Non-hematologic toxicity dose reductions for 5-AZA and ATRA**

NCI CTC Grade	5-AZA	ATRA
0-2	No change from original starting dose	No change from original starting dose
3 -4	Hold until resolved to $\leq$ Grade 2, then reduce to 30 mg/m^2	Hold until resolved to $\leq$ Grade 2, then reduce to 34 mg/m^2
Second episode of grade 3 or 4 toxicity	Remove subject from trial	Remove subject from trial

The administration of 5-AZA will be reported in a log book by the clinical trial staff. All patients will receive a study medication diary to log medication administration and adverse events for both 5-AZA and ATRA (See Appendix A).

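### After a second grade 3-4 episode of the same type, section 8.1 re-doses at half the original dose while section 6.2 stops treatment, and no precedence is stated

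*Combined protocol and SAP*

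**What the plan says.** Section 8.1, in the statistical chapter, covers all grade 3-4 toxicity without separating types. Therapy is held until grade 2 or better, and then "The dose will then be reduced by 25% of original for each episode". It continues: "A maximum of 2 dosage reductions will be allowed. The third occurrence will result in removal of the patient from the study".

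The dosing chapter separates the types:

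- **Hematologic.** Table 6, titled "Hematologic toxicity dose reductions for 5-AZA", covers 5-AZA only. At a first grade 3 or grade 4 occurrence the instruction is "Do not replace missed doses. Restart next treatment at" 30 mg/m². At the second occurrence it is "Discontinue protocol therapy".
- **Non-hematologic, text.** Section 6.2.2 gives one 25% reduction for each drug, then: "After the second episode, the protocol therapy will be discontinued". It is limited to drug-related events: "For grade 3-4 toxicities related to study drug, 5-AZA will be held until improvement of symptoms to grade 2 or below". Section 8.1 has no such limit.
- **Non-hematologic, table.** Table 7 reduces to 5-AZA 30 and ATRA 34 mg/m². In the row "Second episode of grade 3 or 4 toxicity" it takes the subject out of the trial, under both drugs.

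Three places deal with follow-up. Section 3.1 follows patients for 24 months or until the discontinuation events of section 7.1, which include unacceptable adverse events. The Follow Up Period text in section 7 ends follow-up early only for radiographic progression and/or other cancer-directed treatment. Section 7.1 speaks of study removal and then says that the patient is still followed under the protocol.

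**The concern.** At a second grade 3-4 episode of the same type, one current section of the plan re-doses the patient and another takes him off drug. Three things depend on which is followed:

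- **Safety of the patient.** Section 8.1 would re-expose someone whom the dosing chapter judges should receive no more drug, at dose levels that no dosing table lists.
- **Exposure behind the co-primary safety endpoint.** Two patients with the same toxicity history could receive different amounts of drug.
- **Evaluability.** Section 8.2 replaces patients who do not finish 8 weeks of combination treatment, and section 8.4 requires at least 8 weeks for the efficacy analysis. If the second episode comes before that point, stopping may make the patient replaceable, while re-dosing may keep him among the 20 evaluable.

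A secondary matter is what stopping means. For the same second non-hematologic episode, section 6.2.2 ends the drug and Table 7 ends trial participation.

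**Working it through.** **Inputs.** Starting doses are 5-AZA 40 mg/m² on days 1-5 and ATRA 45 mg/m² daily on days 3-7, in 28-day cycles, for 3 cycles (section 3.1, Table 1 of section 5). The section 8.1 step is 25% of the original dose per episode, at most twice. Table 6, section 6.2.2 and Table 7 allow one step, then stop.

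**Step 1: reproduce the plan's reduced doses.** Dose after k episodes = original × (1 − 0.25k). For k = 1:
- 5-AZA: 40 × 0.75 = 30 mg/m², as in Tables 6 and 7.
- ATRA: 45 × 0.75 = 33.75, which rounds to the 34 mg/m² in Table 7.

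The two sections therefore agree on the size of the first reduction.

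**Step 2: second episode of the same type (k = 2).**

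| Rule | 5-AZA | ATRA (non-hematologic) |
|---|---|---|
| Section 8.1 | 40 × 0.50 = 20 mg/m² | 45 × 0.50 = 22.5 mg/m² |
| Table 6; section 6.2.2 and Table 7 | stopped | stopped |

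Section 8.1 reduces from the original dose, so the level is 50%. It is not the compounded 56% (0.75 × 0.75), which would be 22.5 and 25.3 mg/m².

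**Step 3: why the point is limited to the same type.** Tables 6 and 7 each count their own type of episode, while section 8.1 counts all types together. With one hematologic and one non-hematologic episode, section 6.2 does not clearly stop treatment, so the stop-or-re-dose conflict is clear only for two episodes of one type.

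**Step 4: exposure, as an illustration only.** Assume one grade 3-4 hematologic episode after dosing in each of cycles 1 and 2, recovery in time for the next cycle, and no G-CSF used in place of a reduction (Table 6, footnote a, permits that for low ANC). With 5 dosing days per cycle:
- Planned: 3 × 5 × 40 = 600 mg/m².
- Table 6: 5 × 40 + 5 × 30 = 350 mg/m² (350/600 = 58%).
- Section 8.1: 5 × 40 + 5 × 30 + 5 × 20 = 450 mg/m² (450/600 = 75%).

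The difference is one cycle at half dose, 100 mg/m².

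**Step 5: evaluability.** Eight weeks is 56 days, that is, two 28-day cycles. Section 5.1.6 places the marrow nadir at days 10 to 17. In cycle 2 that is treatment day 28 + 10 = 38 to 28 + 17 = 45, before day 56. A patient stopped then has not finished 8 calendar weeks, so he is replaced and falls outside the efficacy analysis. If two dosed cycles count as 8 weeks, he is evaluable. Under section 8.1 he goes on to cycle 3 and passes 8 weeks on either reading.

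**Step 6: is the monitoring plan affected?** Exact binomial recursion on the section 6.2 rule (2 or more of 5, 3 of 10, 4 of 15, 5 of 20) gives early stopping probabilities of 13.8% at a true rate of 10% and 70.5% at 25%. Table 5 states 14% and 71%. The rule takes its events from Tables 6 and 7 and does not use section 8.1, so nothing there changes.

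**The case against.** The best defense is practical. Section 6.2 is the part of the protocol headed as dose modification, the stopping rule is tied to its tables, and section 8.1 is a summary of endpoints. Staff would probably dose from section 6.2. Safety is analyzed descriptively, and G-CSF may avoid some reductions. All of this stands and limits the practical risk. It does not settle the conflict: section 8.1 is current text, it states a complete rule with its own removal trigger, and no sentence gives section 6.2 precedence.

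On Table 7, section 7.1 uses removal language for patients who stop treatment and still has them followed, and the Follow Up Period text agrees. Table 7 may therefore be loose wording. Section 3.1 points the other way, so a clash remains, but a minor one.

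Three stronger readings are tempting, and the documents do not support them:

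- **That most of the 24-month follow-up would be lost.** This takes Table 7 literally against section 7.1 and the Follow Up Period text.
- **That an exit in cycle 2 costs the primary endpoint.** On the calendar reading, a patient stopped in cycle 2 has not finished 8 weeks and is replaced, whether Table 7 says removal or discontinuation. The effect runs through evaluability.
- **That the 10% and 25% toxicity rates in section 6.2 give the number affected.** They are design rates for a stopping rule that counts recurrent or unacceptable toxicity. They do not forecast first or second same-type episodes.

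**Conclusion.** Wrong as written: an internal inconsistency that should be fixed. At a second grade 3-4 episode of the same type, section 8.1 gives 50% of the original dose and section 6.2 gives none. This rests on the text alone and needs no assumption.

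The size of the consequence is less certain. The documents give no rate for second same-type episodes, though few patients are likely to have one. The contrast of 350 and 450 mg/m² holds only under the timing and G-CSF assumptions stated above. The evaluability consequence arises only when the second episode falls before 8 weeks, and for a cycle 2 episode it depends on how 8 weeks is counted. Sample size, power and the toxicity boundaries are unaffected.

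The Table 7 wording is secondary. Read literally, it would end progression follow-up for a treatment-related reason, but the plan's other follow-up text suggests that this is not intended.

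**What to change.** 1. In section 8.1, delete the sentences on holding, reducing and removing, and refer to section 6.2 with Tables 6 and 7: one reduction, then stop at the second episode of the same type. Keep the drug-relatedness condition where section 6.2.2 has it, for non-hematologic toxicity, and do not extend it to Table 6.
2. In Table 7, change the second-episode entry so that protocol therapy is discontinued and endpoint and safety follow-up continue.
3. In section 3.1, replace the pointer to section 7.1 with the reasons for ending follow-up given under Follow Up Period in section 7, and add patient withdrawal.

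The cost is a protocol wording amendment. The sample size and Tables 4 and 5 stay as they are.
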